8. CLINICAL EVALUATIONS/PRO ASSESSMENTS

The following clinical evaluations will be performed according to the Schedule of Study Events and Section 7.1. The same investigator should complete the evaluations for a

given subject throughout the study. If this becomes impossible a sub-investigator with overlapping experience with the subject and the study should complete the evaluations.

8.1. Body Surface Area (BSA)

The percent BSA affected with psoriasis will be estimated at each study visit. The investigator may use the estimate that 1% BSA is equivalent to the area of the subject's closed hand (palm with fingers held together).

8.2. Static Physician's Global Assessment (sPGA)

The sPGA, previously described by Chow et al¹⁰, is used to determine the overall severity of psoriasis lesions at a given time point. This evaluation is not a comparison with the sPGA at any other visit.

Each attribute will be averaged over the subject's entire body.

8.3. Psoriasis Area Severity Index (PASI)

The PASI is a quantitative rating scale for measuring the severity of psoriatic lesions based on area coverage and plaque appearance, which has been shown to have a significant degree of concordance among evaluators.¹¹ PASI analyzes the four regions of the body (head, trunk, upper and lower limbs)

and BSA affected.

8.4. Itch Numerical Rating Scale (I-NRS)

The I-NRS is a simple, [REDACTED] self-administered numeric rating scale [REDACTED] At each visit, subjects indicate itch severity by circling the integer that best describes the worst level of itching due to psoriasis in the past 24 hours on an [REDACTED]

Figure 8-1 I-NRS Questionnaire

8.5. Pain Numerical Rating Scale (P-NRS)

The P-NRS is a simple [REDACTED] self-administered numeric rating scale [REDACTED] that is administered at each visit. Subjects indicate skin pain severity by circling the integer that best describes the worst level of skin pain due to psoriasis in the past 24 hours on an [REDACTED]

8.6. Scaling Numerical Rating Scale (S-NRS)

The S-NRS is a simple, [REDACTED] self-administered numeric rating scale [REDACTED] that is administered at each visit. Subjects indicate scaling severity by circling the integer that best describes the worst level of scaling due to psoriasis in the past 24 hours on an [REDACTED] scale [REDACTED]

8.7. Psychological General Well-Being Index (PGWB)

The PGWB is a self-administered validated psychometric instrument that measures a person's emotional well-being.¹² It is specifically designed to be suitable for assessing psychological well being in the general medical population as opposed to a psychiatric population. The 22 questions of the PGWB [REDACTED]

[REDACTED] is graded on a Likert scale, which is commonly used in psychometric questionnaires where the answers range from strongly agree to strongly disagree with gradations in between. Total scores range from 0 to 110, with higher scores indicating better psychological well being. This instrument has been validated and used in many countries on large samples of the general population and on various subsets of medical patients.

8.8. Dermatology Life Quality Index (DLQI)

The DLQI is a self-administered and user-friendly validated questionnaire used to measure the health-related quality of life of adult patients suffering from a skin disease.¹³ It consists of [REDACTED] questions concerning patients' perception of the impact of skin diseases on different aspects of their health related quality of life over the last week. It has been validated for adult dermatology patients aged 16 years and older. [REDACTED]

[REDACTED]
[REDACTED]
[REDACTED]
[REDACTED]
[REDACTED]
[REDACTED]
[REDACTED]
[REDACTED] higher scores mean
greater impairment of patient's QoL.

8.9. Work Productivity and Activity Impairment Scale (WPAI-PSO)

The WPAI is a validated, subject-reported quantitative assessment of the amount of absenteeism, presenteeism and daily activity impairment attributable to general health or a specific health problem.¹⁴ The WPAI has been validated to specifically quantify work impairments for numerous diseases and the WPAI:PSO was created specifically for administering to patients with psoriasis.¹⁵ WPAI surveys were analyzed based on

published algorithms to determine the following: current employment status, absenteeism [REDACTED] presenteeism [REDACTED] total activity impairment [REDACTED] and total work productivity [REDACTED] impairment [REDACTED] [REDACTED] higher scores representing greater impairment (worse outcomes).

8.10. Treatment Satisfaction Questionnaire for Medication (TSQM)

The TSQM is a general measure of treatment satisfaction with medication, suitable for use across a wide variety of medication types and illness conditions. The [REDACTED] TSQM Version 1.4 is a reliable and valid instrument to assess patients' satisfaction with medication, providing scores on four scales – side effects, effectiveness, convenience and global satisfaction. [REDACTED]

8.11. Tildrakizumab Overall Satisfaction

The Tildrakizumab Overall Satisfaction Scale is a simple, [REDACTED] self-administered numeric rating scale [REDACTED] that is administered at each visit starting at [REDACTED]. Subjects indicate their overall satisfaction with the use of tildrakizumab as well as on specific areas by circling the integer that best describes their experience on an [REDACTED] scale [REDACTED]. [REDACTED] specific areas assessed are:

- Improvement in symptoms
- Speed of symptom improvement
- Frequency of taking the medicine
- Side effects experienced, if any

8.12. Patient Happiness with Psoriasis Control

The Patient Happiness with Psoriasis Control assessment is a simple, [REDACTED] self-administered numeric rating scale [REDACTED] that is administered at each visit. Subjects indicate their overall happiness with psoriasis control by circling the integer that best describes their experience on an [REDACTED]. [REDACTED]

8.13. Full-Body Photography (excluding face)

Full-body photographs will be taken on consenting subjects. Clinical photographs should be standardized using a solid color background and consistent subject positioning and lighting. Approximately six views should be taken; full front, full back and four half-body views, ensuring that all non-head areas affected by psoriasis are

captured. Subjects who refuse to undergo full-body photography may still be enrolled in the study.

9. Laboratory Tests

9.1. Pregnancy Tests

A serum pregnancy test must be performed on all female subjects of child-bearing potential at Visit 1. A UPT will be performed in women of childbearing potential at all visits where study article is administered. The UPT used must have a minimum sensitivity of 25mIU of β -hCG/mL of urine. Please see Schedule of Study Events for all subsequent UPTs. The investigator will report the UPT results on the CRFs, in the subject's medical records and in any independent records maintained at the study site. Subjects with a positive pregnancy test at Visit 1 or prior to the first dose of test article will not be allowed to enter the study (screen failure). Subjects with a positive pregnancy test any time after the first dose of test article will not receive further test article; however subjects should continue with non-treatment follow-up visits. All pregnancies should be immediately reported to the medical monitor and followed through to resolution (i.e., delivery, miscarriage, or abortion). The report should be submitted within the 24 hours of knowledge.

9.2. Laboratory Safety Tests

Laboratory tests for hematology, blood chemistry, and virology/HIV [REDACTED]
[REDACTED] Blood samples for laboratory tests are to be taken prior to first administration of test article and should be performed according to standard laboratory procedures. Followup labs for chemistry, blood count and virology beyond screening can be done at the clinical judgment of the investigator.

10. END OF STUDY (EOS) CRITERIA

At the end of each subject's participation in the study, the investigator will complete an End of Study form for all completed and discontinued subjects.

10.1. Completion of the Study

Subjects who complete the treatment as specified in the protocol and who complete the End of Study evaluations will be considered to have completed the study.

10.2. Subject Discontinuation

A subject may be withdrawn from the study prior to completion for any of the following reasons:

- Whenever the subject decides it is in the subject's best interest to withdraw. NOTE: if the subject decides it is in the subject's best interest to withdraw due to an AE then it should be classified as withdrawal due to an AE.
- Whenever the investigator decides it is in the subject's best interest to be withdrawn

- AEs
- Worsening of condition or treatment failure (in the opinion of the investigator)
- Intercurrent illness which may, in the investigator's opinion, significantly affect assessment of clinical status
- Noncompliance
- Lost to follow-up
- Sponsor administrative reasons

If a subject withdraws prematurely during the treatment period, complete the CRF for the appropriate visit, then complete the End of Study CRFs.

10.3. Screen Failures

If a subject is a screen failure at Visit 1, complete the Screen Failure CRF.

11. SAFETY

11.1. Adverse Events (AE)

An adverse event (**AE**) is defined as any untoward medical occurrence associated with the use of a drug in humans, whether or not considered drug related. An AE can therefore be any unfavorable and unintended sign (including an abnormal laboratory finding), symptom, or disease temporally associated with the use of the drug without any judgment of causality.

Information on the medical condition of subjects should begin following the subject's written consent to participate in the study and a medical history should be taken at screening. During any wash out and baseline periods, any changes in the health of subjects should be recorded as changes in medical history unless an event occurred as a result of a study-related procedure and is unanticipated; where in such cases, the event should be recorded as an adverse event and reported to the Institutional Review Board (IRB) as an "unanticipated problem" in accordance with local procedures. Other changes in subject health information becomes AE data when the subject begins dosing with the test article and therefore AE data should be collected from the date of the first dose of test article. These data are considered treatment-emergent AEs.

Timely and complete reporting of all AEs assists the Sponsor in identifying any untoward medical occurrence, thereby allowing:

- 1) protection of the safety of study subjects;
- 2) a greater understanding of the overall safety profile of the test article;
- 3) recognition of dose-related test article toxicity;

- 4) appropriate modification of study protocols;
- 5) improvements in study design or procedures; and
- 6) adherence to worldwide regulatory requirements.

AEs may be either spontaneously reported or elicited during questioning and examination of a subject. The investigator will instruct the subject to report any adverse events that may occur during the study. At each visit, the investigator should ask the subject, in non-directive fashion, about any change in the subject's overall condition since the previous visit. If known, the investigator should report the diagnosis of the underlying illness or disorder, rather than its individual symptoms.

All AEs must be completely recorded on the AE CRF and include the following:

- **Date of onset**
- **Location of the event – specify whether within affected region**
- The **Severity** of the event. Record the maximum intensity taking into account the possible range of the intensity of the event, using the following definitions:

SEVERITY	
Mild	Adverse event noticeable by the subject but did not interfere in a significant manner with the subject's normal functioning; remedial therapy may have been given.
Moderate	The adverse event was sufficiently intense to produce some impairment of functioning; remedial therapy may have been given.
Severe	The adverse event produced a significant impairment of functioning or incapacitation; therapy was needed.

- Categorize the Relationship to Study Treatment of the AE, as defined below:

RELATIONSHIP	
Not Related:	Concomitant illness, caused by other drug, procedure, accident or event with no reasonable association with treatment.
Unlikely:	An event that does not follow a reasonable temporal association sequence from administration of the test article; that does not follow a known or expected response pattern to the test article, or most likely was caused by the subject's clinical state, other drug, procedure, or other causes, because of their known effects.
Possibly:	An event that follows a reasonable temporal sequence from administration of the test article; follows a known or expected response pattern to the test article; but may have been produced by the subject's clinical state or by other drugs or procedures administered to the subject, or by other causes.
Probably:	An event that follows a reasonable temporal sequence from administration of test article; follows a known or expected response pattern to the test article; is confirmed by improvement on stopping or reducing the dosage; cannot be reasonably explained by the known characteristics of the subject's clinical state or other drugs, procedures or other causes.
Definite:	An event that follows a reasonable temporal sequence from administration of test article; follows a known or expected response pattern to the test article; is confirmed by improvement on stopping or reducing the dosage, and reappearance of the event on repeat exposure (rechallenge).

- Determine the **Action Taken with Study Treatment** due to the AE using the definitions below:

[REDACTED]	[REDACTED]

[REDACTED]

[REDACTED]	[REDACTED]

[REDACTED]

[REDACTED]	[REDACTED]

Subjects experiencing AEs that cause interruption or discontinuation of test article, or those experiencing AEs that are present at the end of their participation in the study should receive follow-up as appropriate. If possible, report the outcome of any AE that caused permanent discontinuation or that was present at the end of the study particularly if the AE is considered by the investigator to be treatment-related (i.e., definitely, probably, or possibly related to test article).

- Determine if the event is considered **Serious** based on the definitions in Section 11.2.
- Record whether the event caused Study Discontinuation.

An **adverse reaction** is any AE caused by a drug. Adverse reactions are a subset of all suspected adverse reactions for which there is reason to conclude that the drug caused the event. For the purposes of prescription drug labeling, the term adverse reaction means an undesirable effect, reasonably associated with the use of a drug that may occur as part of its pharmacological action or may be unpredictable in its occurrence.

A **suspected adverse reaction** is any adverse event for which there is a reasonable possibility that the drug caused the event.

For the purposes of IND safety reporting, “reasonable possibility” means there is evidence to suggest a causal relationship between the drug and the adverse event. A suspected adverse reaction implies a lesser degree of certainty about causality than adverse reaction, which means any adverse event caused by a drug.

An adverse event or suspected adverse reaction is considered “unexpected” if it is not listed in the investigator brochure or is not listed at the specificity or severity that has been observed; or, if an investigator brochure is not required or available, is not consistent with the risk information described in the general investigational plan or elsewhere in the current application. For example, under this definition, hepatic necrosis would be unexpected (by virtue of greater severity) if the investigator brochure referred only to elevated hepatic enzymes or hepatitis. Similarly, cerebral thromboembolism and cerebral vasculitis would be unexpected (by virtue of greater specificity) if the investigator brochure listed only cerebral vascular accidents. “Unexpected,” as used in this definition, also refers to adverse events or suspected adverse reactions that are mentioned in the investigator brochure as occurring with a class of drugs or as anticipated from the pharmacological properties of the drug, but are not specifically mentioned as occurring with the particular drug under investigation.

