to the Medical Monitor/Project Manager and the Sponsor's PV department by email or confirmed facsimile transmission. These include those SAEs listed in the protocol or investigator brochure and must include an assessment of whether there is a reasonable possibility that the drug caused the event.

If only limited information is initially available, follow-up reports are required. Should the investigator become aware of a SAE (regardless of its relationship to test article) that occurs within 30 days after stopping the test article, the SAE must be reported in accordance with procedures specified in this protocol. In the event of death, if an autopsy is performed, a copy of the report should be sent to the Sponsor, if available.

As required, the Sponsor will notify participating investigators of all suspected adverse reactions that are serious and unexpected. This notification will be in the form of an IND safety report of potential serious risks as soon as possible but no later than 15 calendar days after the Sponsor determines that the information is "reportable" according to the criteria listed in 21 CFR Section 312.32. These are:

- i) Serious and unexpected suspected adverse reactions,
- ii) Findings from other studies including epidemiological studies, pooled analyses or other clinical studies that suggest a significant risk in humans exposed to the test articles,
- iii) Findings from animal or in vitro tests that suggest a significant risk to humans exposed to the test articles, or reports of significant organ toxicity at or near the expected human exposure, and
- iv) Clinically important increases in the rate of occurrence of serious suspected adverse reactions.

Upon receiving such notices, the investigator must review and retain the notice with the Investigator Brochure and immediately submit a copy of this information to the responsible IRB according to local regulations. The investigator and IRB will determine if the informed consent requires revision. The investigator should also comply with the IRB procedures for reporting any other safety information. Where required, submission of safety updates by the investigator to Health Authorities should be handled according to local regulations.

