8.11.2 Adverse Events

AEs will be coded using the Medical Dictionary for Regulatory Activities (MedDRA). Verbatim terms will be mapped into a MedDRA system organ class (SOC) and preferred term (PT). For all AE summaries, if a subject has more than one AE within a PT, the subject is counted once in that preferred term. If a subject has more than one AE within a SOC, the subject is similarly counted once in that SOC.

The number and percentage of unique subjects reporting each TEAE will be summarized by SOC and PT. The number and percent of unique subjects reporting each treatment-emergent AE will also be summarized by SOC, PT, and maximum severity (mild, moderate, severe) and closest relationship to test article (not related, unlikely, possibly, probably, definitely).

SAEs, if any, will be summarized by SOC, PT and treatment group.

AE listing will be provided and CTCAE grade will be included.

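### All three related categories of the causality scale require a known or expected response pattern, so a truly novel reaction with plausible timing cannot be rated related.

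*Protocol*

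**What the plan says.** The RELATIONSHIP table in Protocol 11.1 defines five categories.

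- Possibly: timing is reasonable and the event "follows a known or expected response pattern to the test article; but may have been produced by" the subject's condition or other causes.
- Probably: timing is reasonable and the event "follows a known or expected response pattern to the test article; is confirmed by improvement on stopping or reducing the dosage; cannot be" reasonably explained in another way.
- Definite: timing is reasonable and the event "follows a known or expected response pattern to the test article; is confirmed by improvement on stopping or reducing the dosage, and reappearance" on repeat exposure.
- Unlikely: timing is not reasonable; the event is one "that does not follow a known or expected response pattern to the test article, or most likely was caused by" something else.
- Not Related: another cause, with no reasonable association with treatment.

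The text after the table describes an event as "treatment-related (i.e., definitely, probably, or possibly related to test article". The same section defines a suspected adverse reaction by a reasonable possibility of drug causation, accepts that an adverse reaction may be unpredictable, and judges expectedness against the Investigator's Brochure. Under Protocol 11.2, "the Sponsor will notify participating investigators of all suspected adverse reactions that are serious and unexpected".

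In the SAP, causality is part of the safety endpoint (3.3). Section 7.1 lists the five category names without criteria, so the protocol definitions govern. Section 8.11.2 tabulates TEAEs by "closest relationship to test article (not related, unlikely, possibly, probably, definitely".

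**The concern.** Whether a drug caused an event and whether the event was already known are separate questions. The definitions of suspected and unexpected reactions in Protocol 11.1, and the notification rule in 11.2, keep them apart. The relationship table merges them by making a known or expected pattern a condition of every related rating.

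The study is single-arm and open-label, with long-term safety among its objectives. No comparator can reveal an excess of a new event, so investigator attribution carries more weight than it would in a controlled trial. If sites apply the table literally, the related categories can hold only reactions that fit a pattern already known or expected. Protocol 11.1 also stresses reporting the outcome of unresolved or treatment-ending events when they are considered treatment-related, so the rating affects follow-up as well as tabulation.

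**Working it through.** The plan gives no figure to reproduce. The check sets the category definitions side by side and runs example events through them.

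| Category | Timing | Known or expected pattern | Further criteria | Counted as treatment-related |
|---|---|---|---|---|
| Not Related | No reasonable association | Not mentioned | Another cause | No |
| Unlikely | Not reasonable | Absent | Or most likely another cause | No |
| Possibly | Reasonable | Required | May have another cause | Yes |
| Probably | Reasonable | Required | Improves on stopping or reducing; no other reasonable explanation | Yes |
| Definite | Reasonable | Required | Improves on stopping or reducing; recurs on rechallenge | Yes |

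The pattern criterion appears in 3 of 3 related categories, and 0 of 3 give an alternative to it. Nothing visible in the section lets an investigator waive it for a first-time reaction.

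**Event A: novel, plausible timing, no better explanation.** It fails Possibly, Probably and Definite on the pattern criterion. It does not fit Not Related, because there is a reasonable association and no other cause. If absence of a pattern is enough on its own, it is Unlikely. If Unlikely also needs implausible timing, it has no category. On both readings it is not counted as related.

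**Event A against the protocol's other definitions.** It can be a suspected adverse reaction, since that needs only a reasonable possibility. It can also be unexpected, being absent from the brochure. The 11.2 notification rule presupposes that such an event exists, but the table has no related category for it.

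**Event B: known pattern, plausible timing, resolves between injections, no other explanation.** Injections are at Weeks 0, 4, 16, 28, 40 and 52, so the gaps are 4 weeks and then 12 (16 − 4, 28 − 16, 40 − 28, 52 − 40). Resolution within a gap involves no stopping or reduction unless the gap itself counts as stopping, which the protocol does not say. The event then fails Probably and Definite. Read literally it also fails Possibly, because no other cause may have produced it.

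**Illustration of size for event A.** Assume all 60 subjects are followed to Week 64 and every site applies the table literally. The incidence p is an assumption; the documents give none.

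- p = 5%: expected cases 60 × 0.05 = 3; chance of at least one 1 − 0.95^60 = 0.954.
- p = 2%: expected cases 60 × 0.02 = 1.2; chance of at least one 1 − 0.98^60 = 0.702.

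In either case the number that can be rated related is 0, which follows from the wording and not from p. If 3 cases occur, the table by system organ class and preferred term still shows 3/60 = 5%.

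**The case against.** Five arguments go the other way.

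1. *Unexpected is a different test.* A reader might infer that no unexpected reaction can be rated related. The documents do not support that. Protocol 11.1 also calls events unexpected when they are known for the drug class, anticipated from pharmacology, or more severe or specific than the brochure states. Many of these could be said to follow a known or expected pattern, a term the protocol leaves undefined. This argument stands and confines the point to truly novel reactions.

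2. *Unlikely is not the assured destination.* A reader might infer that the table sends novel reactions to Unlikely by rule. As event A shows, they may instead fit nowhere and be left to judgement. This also stands. Downward bias in the related categories is therefore a risk of literal use and not an established result.

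3. *Serious events are covered.* A reader might infer that expedited reporting is blocked. It is not. Under Protocol 11.2 all SAEs are reported within 24 hours whatever their relationship; the investigator, medical monitor and sponsor pharmacovigilance assess causality; and the written report must address reasonable possibility separately. What remains is that a site may have to record two differing causality judgements for one event. Non-serious events have no second route.

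4. *Overall incidence is intact.* A reader might infer that the study would report 0% where the truth is about 5%. SAP 8.11.2 counts every TEAE by organ class and preferred term regardless of relationship, lists all AEs, and defines no pooled drug-related rate. This stands; only the relationship breakdown is exposed.

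5. *Dechallenge and rechallenge rarely change the related count.* An event that misses Definite or Probably usually drops to Possibly, which is still related, and six injections allow repeat exposure for events that do not preclude continuation. This stands too, except for event B.

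None of these arguments supplies a related category for a novel, non-serious reaction.

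**Conclusion.** The point holds for truly novel reactions with plausible timing. The table in Protocol 11.1 gives them no related rating, which contradicts the reasonable-possibility standard in that section, its acceptance that reactions may be unpredictable, and the assumption in 11.2 that a reaction can be both suspected and unexpected. The effect is mainly on non-serious AEs, on the relationship part of the safety endpoint and its table, and on outcome follow-up that depends on the rating. Total TEAE incidence and SAE reporting do not depend on it.

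The size cannot be fixed from the documents: it depends on whether a novel reaction occurs and how literally sites read the table. The gap for event B is secondary and rests on a literal reading of Possibly.

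**What to change.** Amend the RELATIONSHIP table in Protocol 11.1:

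- Remove the pattern criterion as a requirement for Possibly, Probably and Definite, and its absence as a stand-alone criterion for Unlikely.
- Base Possibly on the protocol's own reasonable-possibility standard, so that it no longer depends on a competing cause.
- Assess expectedness separately against the Investigator's Brochure, as 11.1 already defines it.
- Make dechallenge and rechallenge supportive evidence where applicable.

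The five categories in SAP 7.1 and 8.11.2 can stay, with a reference to the amended definitions. If AEs have already been rated, investigators should review those rated Unlikely, or left unclassified, for lack of a known pattern. Keep the rating first recorded, and report both.

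The cost is an IRB-approved amendment (Protocol 13.4), some re-review work that adds retrospective judgement in an open-label study, and possibly a slightly higher related-AE count. Adverse events are in the Week 28 interim analysis (SAP 8.10.2), so final relationship tables may differ from interim ones; reporting both ratings makes that difference traceable. No new data are needed.
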